Clinical Trial # NCT02928172
ID: Pro00043738 Date: 9/27/2016

STUDY PROTOCOL

Monitoring the responses to nociceptive stimuli during general anesthesia based on electroencephalographic signals, an observational study.

INSTITUTION

Department of Anesthesiology
Cedars-Sinai Medical Center in Los Angeles
[name]
[name]

HYPOTHESIS

The Electroencephalogram (EEG), a direct measurement of brain activity, could contain information related to the probability of response of the patient to a noxious stimulation as well as being sensitive to changes in opioid concentrations. For this reason, the hypothesis is that there is a statistically measurable correlation between qNOX and rough clinical signs of insufficient anti-nociception such as movements during Laryngeal Mask Airway (LMA) insertion, skin Incision, LMA removal. It will reduce the problem of anticipating the nociception in patients undergoing general anesthesia.

STUDY OBJECTIVES

- 1) to compare two indexes of hypnosis, the qCON (Quantum Medical, Spain) with the Bispectral index (BIS™) (Covidien, Boulder CO. USA), in patients undergoing surgery under sedation and general anesthesia.
- 2) to assess the qNOX index of pain/nociception (Quantum Medical, Barcelona, Spain) and the qCON index of hypnosis.
- 3) to assess qNOX reliability as a specific indicator of response to nociceptive stimulation.

BACKGROUND AND SIGNIFICANCE

[figure not shown]
Monitoring the anti-nociceptive drug effect is useful because a sudden and strong nociceptive stimulus may result in untoward autonomic responses and muscular reflex movements ⁽¹⁾. Unopposed stimulation may also 'overrule' a state of stable unconsciousness, with resultant awakening and awareness. The traditional clinical use of systolic or mean blood pressure is actually still one of the methods in everyday use for this monitoring purpose ⁽²⁾. Another cornerstone is the experience of which drugs and doses are effective in attenuating nociception. Alpiger and colleagues found that simple end-tidal monitoring of sevoflurane was a better predictor of nociceptive response than Auditory Evoked Potential ⁽³⁾.

Thus, monitoring the state of anti-nociception with objective, non-clinical methods is still in a state of testing and development, without well-documented and proven methods for consistent 'no-fuss' clinical daily use. Some methods, like those using systolic blood pressure, are based on the reduced sympathetic response from the Central Nervous System (CNS) when in a state of drug-induced anti-nociception during concomitant surgical stress. These include the pulse plethysmogram amplitude,⁽⁴⁾ heart rate variability and/or amplitude,⁽⁵⁻⁷⁾ pupillometry,⁽⁸⁾ muscle tonus and skin conductance.⁽⁹⁾ They all have limitations in interpretation, as the state of

sympathetic tone is strongly influenced by numerous factors, including hypovolemia, vasopressors, atropine and patient positioning. In addition, sympathetic tone is very unspecific in the awake or lightly sedated patient, as mood and subjective feelings have a strong impact.

Attempts are also been made on using the EEG for monitoring of anti-nociception. This approach has been challenged as difficult,⁽¹⁰⁾ as most of the antinociceptive drugs effects are in the periphery, the medullary cord⁽¹¹⁾ or deeper cerebral layers, far from the EEG signals derived from the frontal cortex. However, EEG is a 'mirror' of what is going on in other parts of the CNS and peripheral nervous system. One problem is to elucidate how the EEG signals may be used in a sensitive and specific way to reflect anti-nociception. Concepts such as response-entropy,⁽⁹⁻¹²⁾ Composite Variability Index⁽¹³⁾ and BIS variability score⁽⁹⁾ have been tested and launched.

Quantum Medical has an EEG-based algorithm with two outputs: the qCON for unconsciousness and the qNOX for anti-nociception.⁽¹⁴⁾ This means that calculates and displays two indices. One, the qCON, is designed to provide information about the depth of the hypnotic state, similar to that provided by the BIS™ and Sedline™ monitor (Masimo, Irvine CA). The second index, the qNOX, is designed to provide information about the depth of the antinociceptive state. The qCON has shown a comparable performance with BIS, and qNOX has proved correlation with rough clinical signs of insufficient antinociception, such as movements during LMA insertion, laryngoscopy and tracheal intubation¹⁴. Figure 1 shows an example of the mentioned signals during a general anesthesia procedure.

Example of the three electroencephalographic indexes (Bis, qCON and qNOX).

STUDY METHODS:

[figure not shown]
I. Recruitment:

- a) Study investigators will review the surgery schedule 10 days ahead and contact the potential subjects by email or mail with an invitation to participate in this study. If we don't get back from them potential subjects in 5 days we contact them by phone, following the phone consent script, and ask them if they are interested in the research study and if they agree we will answer all the questions and concerns and obtain the consent over phone or when the subjects come to the pre-operative area the day of the surgery. With the subjects approval, we will mail or email the study material packet containing the HIPAA and the informed consent form.
- b) Investigators will explain the study protocol including the potential benefits and potential risks. Patients will be told that they have the right to choose or refuse the study without any loss and any penalty because their participation in this study is voluntary.
- c) Only patients who have provided their written consent and indicated that they have been introduced to the study prior to meeting with the anesthesiologists on the day of surgery; will be able to participate and undergo screening procedures for this study.
- d) Screening procedures will make sure patients meet all inclusion criteria. If patient meets all inclusion criteria, they will be accepted into the study.

II. Procedure for the preparation of the medical devices

- 1) The study investigator will prepare

- a) the PC.
- b) the qCON-qNOX monitor and the BIS monitor (power supply unit and cables).
- c) the skin preparation unit for each patient.
- d) sensors for the qCON-qNOX and BIS monitor:

- 2) The patient's cable will be connected to the qCON-NOX monitor and the qCON FTDI chip cable to the laptop USB port.
- 3) The qCON-NOX Display PC software will be checked if opens correctly, marks "Lead off" (because the electrodes are disconnected) and its files are saved. In addition, date and time will be well-adjusted.
- 4) After the electrodes are placed the qCON-NOX data will be displayed in one PC.

Steps:

- a) open the software and select a COM port,
- b) press the start button,
- c) verify that files are being saved,
- d) verify that the impedances are below 15 and that the program state is running,

On the upper side are 5 parameters with different colors:

EMG: Electromyography signal power in a frequency band.

BSR (Burst suppression rate): % of time with isoelectric EEG in a window of 30 s.

SQI (Signal quality index): quality indicator signal. During acquisition this value should remain as high as possible (close to the value 100).

qNOX: index of pain.

qCON: index of anesthetic depth.

[figure not shown]
5) qCON-NOX Display PC during signal acquisition.

III. In the preoperative holding area:

[figure not shown]
- 1) Collection of a detailed medical history including demographic information (e.g., age, weight, height, gender, ethnic origin).
- 2) Written informed consent will be obtained by one of the investigators.

IV. During the intraoperative period:

- 1) Standard monitors: automatic blood pressure cuff, three-lead electrocardiogram, capnograph, pulse oximeter and BIS monitor will be applied.
- 2) The electrodes of the qCON-NOX monitor also will be placed, in a clean skin area of the forehead. The qCON-NOX monitor has a sensor with three electrodes: red, yellow and green. qCON-NOX monitor sensors placement: at left side of the head, like is showing on the next pictures:

- 3) Place the BIS sensor on the patient and prepare the Bispectral Index monitor.

During the recording process:

- 4) When the recording process (BIS and qCON-NOX monitors) starts, the qCON-NOX Display PC will make an impedance measurement. If impedance values are high,

electrodes should be repositioned. In case they are repositioned twice and impedances remain higher than 15 kΩ, the patient will be withdrawn.

5) Data collection of the standard of care Anesthesia Technique chosen by the anesthesiologist:

I Premedication Standard Anesthesia Procedure:

Midazolam 20 ug/kg IV (1-2 mg IV)

II General Anesthesia with LMA

- a. Induction with Fentanyl 50-100 Mcg,
- b. Propofol, 1.5-2 mg/kg IV, with lidocaine, 30-50 mg IV followed by
- c. Sevoflurane or desflurane 3% +
- d. propofol 50-100 µg/kg/min for maintenance of anesthesia
- e. For purposeful movements:
 - i. Propofol 20-50 mg IV
 - ii. Fentanyl 25-50 mcg, and if movements persist
 - iii. Increase the inspired sevoflurane or desflurane concentration by 1-2%
- f. Local anesthetics (lidocaine 2% and/or bupivacaine 0.5%) injected by surgeon as needed for analgesia locally during the operation
- g. Ondansetron, 4 mg IV, and dexamethasone, 4 mg IV, administered before the end of surgery for antiemetic prophylaxis
- h. Analgesics chosen by the anesthesiologist, will be given during the surgical procedure

V. At the end of surgery:

- 1) Record the time of the anesthetics discontinuation at skin closure
- 2) The exact time of the stimulation (verbal/noxious) and response of the patients during the awakening process must be recorded in the qCON-NOX Display Software.
- 3) The monitors will be disconnected from the patient once he/she is awake.
- 4) Patients will be transferred to the recovery room.

VI. Patient perioperative evaluations and data collected:

- 1) Response to noxious stimuli from induction to emergence (such as insertion of laryngeal mask [LMA placement], skin preparation, incision, skin suture, surgical events, closure, LMA removal or any other noxious stimuli.
 - a) Number of coughs
 - b) Cough severity will be graded as mild (1-2), moderate (3-5), or severe (>5)

- c) Bucking
- d) Gasps
- e) Increase of heart rate, blood pressure and respiratory rate
- f) Movements (movement in the period of 1 minute after applying the stimuli will be interpreted as a positive response to one of the nociceptive stimuli)

2) Vital signs (including MAP, and HR), at 5-10 min intervals throughout the intraoperative period

3) Dosages of anesthetics, analgesic, sedatives, local anesthetics, IV fluid therapy during the operation

4) Rescue bolus doses of propofol and/or fentanyl to treat coughing and/or movements.

5) Duration of surgery (from skin incision until closure) and anesthesia (from IV induction until discontinuation of the anesthetic drug)

6) BIS and qCON-qNOX monitors will be recorded throughout the intraoperative period and the recorded data will be archived for subsequent analysis. Also, the side where the BIS and qCON-qNOX electrodes were placed.
Anesthesiologists will be blind to qCON-qNOX monitor; this one will be covered during all the procedure.

7) The exact time of the following stages of the surgery must be recorded in the qCON-qNOX Display Software (Also will be recorded in the data collection sheet):

- a) assessment of the level of consciousness of the patient using OAAS scale, ⁽¹⁵⁾
- b) start of induction and end of induction,
- c) start and end of laryngeal mask placement,
- d) start and end of infusion pumps,
- e) response to noxious stimuli
- f) start and end of surgery
- g) emergence from anesthesia

8) Duration of surgery (from skin incision until closure)

9) Duration of anesthesia (from induction until discontinuation of the anesthetic drug)

10) LMA removal time

11) BIS and qCON-qNOX values at the time of rescue medication

12) Recovery times from discontinuation of anesthetic drugs until:

- a) eye opening
- b) following verbal commands

- c) orientation to person, place and time
- d) meeting discharge criteria (from PACU)

13) Requirements for “rescue” analgesic medication and antiemetic medication will be recorded before discharge.

14) Any side effects during the perioperative period.

15) Recall

16) Pain score at PACU

VII. DATA ANALYSIS

A power calculation will be pursued based on the following assumptions. We decide to have a power of 0.9 and a level of significance of 0.05. Previous experience showed that the standard deviation (SD) of the qCON is less than 24, and we consider a change of 15 as significant, hence the standardized difference is $15/24 = 0.625$. According to Altman, ⁽¹⁶⁾ with these conditions the necessary sample size is 54 patients. Considering that some patients might be withdrawn because of high impedances of any of the monitors or any other technical issues, the number of patients to be monitored is 60.

The prediction probability (Pk) ⁽¹⁷⁾ will be used to assess the ability of the Bis, qCON and qNOX to predict the OAAS score and response to noxious stimulation. The Pk and its standard error (SE) will be calculated using the jackknife estimate which has the advantage that the variance can be estimated by the Student's t-distribution. The normal distribution using a Lilliefors test will be tested before using a Student's t-test (paired) to test for significance at $P < 0.05$. Also, the correlation between qCON-NOX, BIS, sevoflurane and desflurane drugs will be estimated using Pk. Finally, the Bland–Altman plot for $(qCON+Bis)/2$ vs. $(Bis-qCON)$ will be presented.

VIII. INCLUSION AND EXCLUSION CRITERIA

1. Inclusion Criteria

Subjects may be included in the study only if they meet all of the following criteria:

- 1) Patients scheduled to undergo general surgical procedures with general anesthesia/LMA.
- 2) Willingness and ability to sign an informed consent document.
- 3) 18 – 80 years of age.
- 4) ASA Class I – III adults of either sex.

2. Exclusion Criteria

Subjects will be excluded from the study for any of the following reasons:

- 1) Inability to consent

3. Withdrawal criteria

Subjects will be withdrawn from the study for the following reasons:

- 1) Electrodes should be changed when patient's skin impedance value exceeds 15 kΩ after conditioning skin properly. If after two changes of electrodes, impedance remains above 15 kΩ, patient will be excluded from the present study.

Observer's Assessment of Alertness/Sedation Scale (OAAS)

Table 1. Observer's Assessment of Alertness/Sedation (OAAS)¹¹

Responsiveness	Speech	Facial Expression	Eyes	Score
Responds readily to name	Normal	Normal	Clear, no ptosis	5
Lethargic response to name	Mild slowing	Mild relaxation	Glazed or mild ptosis	4
Responds to name only if called repeatedly	Slurring	Marked relaxation	Glazed or marked ptosis	3
Responds only after mild prodding	Not recognizable			2
No response to prodding or shaking				1

OAAS is the lowest score in any of the four categories.

OAAS score 5—awake and responds readily to name spoken in normal tone.

OAAS score 4—lethargic responses to name in normal tone.

OAAS score 3—responds only after name is called loudly and/or repeatedly.

OAAS score 2—responds only after name called loudly and mild shaking.

OAAS score 1—does not respond when name is called loudly and mild shaking or prodding.

OAAS score 0—does not respond to noxious stimulation.

REFERENCES

1. J. Raeder. EEG-based monitor on anti-nociception during general anaesthesia: mission impossible? *Acta Anaesthesiol Scand* 2014; 58: 911–913.

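### The only masking rule covers anesthesiologists and the qCON-qNOX monitor; whoever scores OAAS and response to noxious stimuli is left open to seeing an index under test

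*Combined protocol and SAP*

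**What the plan says.** **Masking.** Section VI (perioperative evaluations), item 6, has the only rule: "Anesthesiologists will be blind to qCON-qNOX monitor; this one will be covered during all the procedure". It names one group and one device.

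**Reference standard.** Section VII (Data Analysis) uses Pk to judge how well BIS, qCON and qNOX predict the OAAS score and the response to noxious stimulation. Section VI item 1 lists the response signs: coughs, bucking, gasps, vital-sign increases, and movement within 1 minute of the stimulus. No section says who makes these calls.

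**Where events are logged.** Section VI item 7, whose list includes OAAS assessment and response to noxious stimuli: "The exact time of the following stages of the surgery must be recorded in the qCON-qNOX Display Software", with the addition "Also will be recorded in the data collection sheet". Section V item 2, for emergence: "The exact time of the stimulation (verbal/noxious) and response of the patients during the awakening process must be recorded in the qCON-NOX Display Software".

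**What that software shows.** Section II item 4: "After the electrodes are placed the qCON-NOX data will be displayed in one PC". Then: "On the upper side are 5 parameters with different colors". One of the five is "qNOX: index of pain" and another is qCON. Section II item 1 lists the PC and the qCON-qNOX monitor as separate pieces of equipment.

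**BIS.** Section IV item 1 applies it with the standard monitors: "three-lead electrocardiogram, capnograph, pulse oximeter and BIS monitor will be applied". No cover is mentioned.

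**The concern.** Pk measures agreement between an index and an outcome that a person judges at the bedside. If that person can see the index, doubtful calls may be settled by it, and part of the agreement is then manufactured. Archiving the index data does not help, because the reference is scored live.

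Exposure differs by sign. OAAS grades, bucking, gasps and borderline movement need judgment. Gross movement (the sign named in the Hypothesis), cough counts and measured vital signs need less.

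The comparison with BIS is also affected, but the direction cannot be read from the plan. An anesthesiologist who scores would see BIS and not qCON-qNOX. An investigator at an uncovered PC could see qCON-qNOX, and perhaps BIS as well.

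**Working it through.** The plan gives no figure that depends on masking, so there is none to reproduce. The check has two parts.

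**1. Does the cover in VI.6 reach the scorer?**
- The cover is stated for the monitor. Section II item 1 lists the PC separately, and the indexes are displayed on the PC.
- V.2 and VI.7 require event times in the software on that PC. A fully covered PC would make event entry difficult.
- BIS has no stated cover.
- Neither V.2 nor VI.7 says that the person entering times is the scorer, or when the entries are made.

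So exposure is possible under the plan as written, but not established.

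**2. How large could the bias be?** All inputs are assumptions, not taken from the documents: a yes/no response in p = 30% of stimuli (q = 1 - p); an index that is normal with equal variance in responders and non-responders; true Pk of A = 0.70 or 0.80; and a share w of calls that is borderline and set entirely by whether the seen index lies above its median.

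If the reading seen is the reading analysed, the share of calls scored positive is P = (1-w)p + w/2, and

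observed Pk = [(1-w)²pqA + (1-w)(w/2)(p·a + q·b) + w²/4] / [P(1-P)]

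Here a is the probability that a true responder's index exceeds a borderline event's index from below the median. The term b is the probability that a borderline event's index from above the median exceeds a true non-responder's. For A = 0.70, a = 0.878 and b = 0.815; for A = 0.80, a = 0.932 and b = 0.852.

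Example, A = 0.70 and w = 10%: P = 0.9 × 0.3 + 0.05 = 0.32. The numerator is 0.81 × 0.21 × 0.70 + 0.9 × 0.05 × (0.3 × 0.878 + 0.7 × 0.815) + 0.0025 = 0.1191 + 0.0375 + 0.0025 = 0.1591. The denominator is 0.32 × 0.68 = 0.2176. Observed Pk = 0.731.

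| Borderline share | True 0.70 reads | True 0.80 reads |
|---|---|---|
| 2% | 0.706 | 0.804 |
| 5% | 0.716 | 0.809 |
| 10% | 0.731 | 0.818 |
| 20% | 0.761 | 0.836 |

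If only half of the borderline calls follow the index, the rise roughly halves (0.703-0.731 and 0.802-0.818).

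**A different reading is analysed.** The plan does not say which reading enters Pk. Simulation with the seen and analysed readings correlated within outcome (correlations assumed), over 2-20% borderline:
- correlation 0.8: 0.70 reads about 0.704-0.738, and 0.80 reads about 0.801-0.816;
- correlation 0.5: 0.70 reads about 0.700-0.706, and 0.80 falls from about 0.798 to 0.789. The borderline calls then act mainly as misclassification.

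**OAAS.** With six equally frequent grades and borderline ratings moved one grade toward the index (also assumed), 0.699 reads 0.702-0.726 and 0.800 reads 0.802-0.823 over 2-20%.

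**Two indexes of equal Pk, only one seen and its seen reading analysed.** At within-outcome correlation 0.8 to 0.5, the seen index gains a false advantage of 0.002-0.006 at 2%, 0.005-0.014 at 5%, 0.01-0.03 at 10% and 0.02-0.055 at 20%. If both are seen equally, neither gains on the other, but both rise.

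**Scale.** Take the plan's 54 patients and the three stimuli named in the Hypothesis: 54 × 3 = 162 events. Treated as independent, the standard error (SE) of a single Pk is about 0.038-0.045, and that of a paired Pk difference about 0.026-0.045. The false advantage is then 0.1-0.3 SE at 2-5% borderline, 0.4-0.6 SE at 10% and 0.8-1.2 SE at 20%.

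**The case against.** The strongest reply is that this is silence, not a demonstrated flaw. VI.6 says without exception that the monitor is covered throughout, which could mean hidden from everyone in the room. The software must hold event times, but the plan does not say that scores are entered there or that the entry is made at the moment of scoring. That stands: a reader might infer that the scorer will be unmasked, and the documents do not support it. The wide reading of the cover is weaker, because the sentence is tied to anesthesiologists and the PC is listed apart from the monitor.

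A reader might also infer that Pk will be inflated, or that the new device will be favoured over BIS. Neither follows. The rise depends on the reading seen being close to the reading analysed. The direction against BIS depends on who scores and what that person sees.

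The size is modest for the sign named in the Hypothesis. Gross movement leaves few borderline calls, and at 2-5% the rise of 0.004-0.016 is well below the SE of a single Pk. Nothing in the documents supports 20%. Correlation between stimuli in one patient would enlarge the SEs and make the ratios smaller still.

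Some checks already exist, but they are partial. Vital signs every 5-10 minutes (VI.2) can hardly resolve a 1-minute response, and VI.1e sets no threshold for an increase. Timed eye opening, following commands and orientation (VI.12) give some anchor for OAAS, at emergence only. These do not replace masking of the scorer.

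**Conclusion.** The gap is real and worth closing as a cheap improvement. The plan masks one group to one device, leaves the scorer of the Pk reference unnamed and unmasked, and requires event times in software that displays two of the indexes under test. It does not show that the scorer looks at them.

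If the scorer does, the plausible effect on Pk runs from slightly negative to about +0.06. The upper end needs 20% borderline calls, all following the index, with that same reading analysed. For gross movement the effect is probably small; OAAS grades, bucking, gasps and borderline movement are more exposed. For BIS against qCON the direction is undetermined. All sizes rest on the assumed response rate, borderline share and correlations. This is a bias, so more patients would not remove it, and the existing data offer only weak checks afterwards.

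**What to change.** In section VI item 6, add:
- After the impedance and file-saving checks, the qNOX and qCON fields on the Display PC are covered during the case. SQI, impedance and event entry stay visible as far as the screen layout allows.
- OAAS and response to noxious stimuli are scored by an existing team member. The score is written on the data collection sheet before that person looks at qCON, qNOX or BIS. VI.7 requires only times on that sheet, so the score is a new entry beside them.
- The index values at rescue medication (VI.11) are taken from the archived recordings, not read off a screen.
- BIS stays available to the anesthesiologist. Where the scorer cannot avoid seeing BIS, this is reported as a limitation of the BIS comparison.

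Cost: a few sentences, one extra entry on the sheet and a partial screen cover. The documents do not give the number of investigators present, so it is an assumption that the present team can do this. Downside: the PC operator has SQI rather than the index trace for spotting a signal fault.

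### Section VII does not make the patient the unit for the jackknife SE of Pk or for the paired t-test, so clustering of readings within patients may go unaccounted for

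*Combined protocol and SAP*

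**What the plan says.** Section VII (Data Analysis) makes Pk the main tool: it "will be used to assess the ability of the Bis, qCON and qNOX to predict the OAAS score and response to noxious stimulation". For precision, "The Pk and its standard error (SE) will be calculated using the jackknife estimate". After a Lilliefors check, it plans a Student's "t-test (paired) to test for significance at" P < 0.05. It does not say whether a reading or a patient is left out, what the t-test pairs, or how repeated readings enter. The only unit in the section is in the sample-size sentence: "with these conditions the necessary sample size is 54 patients".

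Section VI describes repeated data in every patient. Item 1 lists LMA placement and then "skin preparation, incision, skin suture, surgical events, closure, LMA removal or any other noxious stimuli", which is seven named types plus a catch-all. Item 1f scores response per stimulus: movement within one minute "will be interpreted as a positive response to one of the nociceptive stimuli". Item 7a adds "assessment of the level of consciousness of the patient using OAAS scale", with no frequency given. The Hypothesis section names three stimuli.

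Two features bear on how alike one patient's responses are. The anesthesiologist chooses technique and analgesics for each patient (section IV, item 5). Section VI, item 4 records "Rescue bolus doses of propofol and/or fentanyl to treat coughing and/or movements".

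**The concern.** A jackknife SE is not defined until the deleted unit is named. In its ordinary form it leaves out one observation at a time, and with these data an observation is naturally read as one stimulus or one OAAS rating. That is valid only if readings from the same patient are independent.

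Here they may not be. A drug regimen chosen per patient may make that patient's responses alike, while rescue after a movement or cough may make the next response less likely. These act in opposite directions, so the error in the SE cannot be signed in advance.

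At stake are the error bars on Pk for qNOX, qCON and BIS, which bear on objective 3, and any comparison judged at P < 0.05, the only significance criterion in the plan. An unstated unit could also be chosen after the results are seen.

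**Working it through.** **1. The plan's own figure.** Inputs from section VII: power 0.9, significance level 0.05 (two-sided assumed), SD 24, change 15, standardized difference 15/24 = 0.625.

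n = 2(1.960 + 1.282)² / 0.625² = 2 × 10.51 / 0.3906 = 53.8, rounded up to 54.

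This reproduces 54, as the per-group number for two independent means. Whether that formula suits this design is a separate matter. Two things count here: the unit is the patient, and the calculation concerns qCON rather than Pk. The documents give no SE of Pk to reproduce.

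**2. The two jackknives.** Pk is the proportion of pairs of readings with different observed states that the index orders correctly, with index ties counted as one half. With K units, the pseudo-value is p_i = K·Pk − (K−1)·Pk(without i), and SE = SD(p_i)/√K. For 54 patients, K is 54 × 3 = 162 or 54 × 7 = 378 if readings are deleted, and 54 (53 df) if patients are.

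**3. SE of one Pk.** Simulated with 54 patients and Pk about 0.71-0.73. The table gives the single-reading SE divided by the true SD, at an assumed within-patient correlation of the index of 0.3 / 0.5 / 0.7:

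| Pattern of states | Ratio |
|---|---|
| Response constant within patient, 6 readings | 0.66 / 0.54 / 0.46 |
| Response partly clustered (latent correlation 0.5), 6 readings | 0.81 / 0.77 / 0.69 |
| Every patient has exactly one response in 2 readings | 1.18 / 1.38 / 1.58 |
| Every patient has exactly three responses in 6 readings | 1.14 / 1.23 / 1.39 |
| Every patient passes through six OAAS levels | 1.12 / 1.14 / 1.04 |

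Coverage of the 95% interval runs from 0.64 (ratio 0.46) to 0.995 (ratio 1.58). Deleting patients gives ratios of 0.94-1.04.

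**4. Error of a nominal 5% paired test on Pk, response to stimuli.** Assumptions: the test compares Pk values; 54 patients; 30% base response; two equally good indices with Pk 0.70 and correlation 0.5 between them; within-patient correlation 0.3 / 0.5 in both index and latent response. After a response, rescue lowers the next latent response by d SD. 4,000 trials per scenario, single-reading deletion:

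| Scenario | 3 stimuli | 7 stimuli |
|---|---|---|
| d = 0 | 6.0 / 7.8% | 8.0 / 14.1% |
| d = 0.5 | 5.5 / 7.1% | 6.3 / 11.9% |
| d = 1 | 4.9 / 5.6% | 5.8 / 9.2% |
| d = 2 | 4.9 / 5.5% | 6.0 / 8.4% |
| Responses not clustered | 4.7 / 5.3% | 5.1 / 6.9% |
| Exactly one response per patient | 2.3 / 0.9% | 2.7 / 1.0% |

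The Monte Carlo SE is about 0.3 points at 5% and 0.6 at 14%. Deleting patients gives 4.3-5.7% throughout. A separate simulation of 1,000 trials per scenario gave, for single readings, 6.9 / 8.5% (3 stimuli) and 9.7 / 15.1% (7) with d = 0, and 4.5-4.9% and 5.8-10.8% with d = 1. Patient deletion gave 3.5-6.7%.

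**5. When the SE for response is too large.** With 3 stimuli and a mean of one response per patient, the share of patients with exactly one response was varied, the rest having none or two (3,000 runs). At correlation 0.3 / 0.5 the error was 2.4 / 1.1% at a share of 100%, 3.5 / 2.7% at 70%, 4.1 / 4.0% at 50% and 5.3 / 5.1% at 30%.

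**6. OAAS.** Assuming every patient is rated at all six levels (Pk about 0.81), single-reading error is 5.5 / 7.7% with one rating per level. It is 10 / 18% with three per level, that is 6 × 3 = 18 ratings per patient (400 trials, Monte Carlo SE up to 2 points). Patient deletion gives 4.2-5.3%.

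**7. If the t-test pairs raw index values.** With m pooled readings per patient and correlation ρ between a patient's paired differences, the variance is understated by 1 + (m−1)ρ. The actual error is 2[1 − Φ(1.96/√(1 + (m−1)ρ))]. For m = 3, ρ = 0.3 the factor is 1.6 and the error 12%. For m = 6, ρ = 0.3 it is 2.5 and 22%. For m = 10, ρ = 0.5 it is 5.5 and 40%. Simulation agrees (12%, 22%, 40%), and one mean per patient gives about 5%.

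**The case against.** The strongest reply is that this is an ambiguity, not a planned error. A reader might infer that single readings will be deleted, but no sentence says so. Deleting patients, analysing each stimulus separately, or taking one pair per patient would all comply and be valid, and patients are the only unit that the plan counts. The source cited for Pk (reference 17) may define the unit; the supplied list ends at 8, so this cannot be checked. All of that stands, and it makes the point conditional. It does not supply the missing unit.

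Three further objections stand and limit the size:

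- The text does not say that the t-test compares Pk values. The power calculation concerns a change in qCON, so the test may concern raw index values. The percentages in step 4 hold only on the first reading.
- With the three stimuli of the hypothesis and a 1 SD rescue effect, the error is about 5-6%. The seven types come from an illustrative list in which skin suture and closure may overlap.
- A reader might infer that the test is conservative whenever patients respond about once on average. Step 5 shows that this is not enough: most patients must respond exactly once, and no passage supports that.

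It is also fair that the study is observational, that no decision rule is tied to P < 0.05, and that the Pk point estimates and the Bland-Altman plot are unaffected.

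**Conclusion.** The concern holds as a conditional one. Nothing carries the patient unit from the sample size into the Pk analysis, and the ordinary single-reading jackknife gives too small an SE when index and response both cluster within patient. If the test compares Pk values, the nominal 5% error becomes about 6-8% with 3 stimuli and 8-15% with 7, without a rescue effect. With a 1 SD effect it is about 5-6% and 6-11%. It is close to 5% if responses do not cluster. For response, the SE is too large only if most patients respond to exactly one stimulus.

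A reader might take the 14% (response) or 18% (OAAS) as the expected error. They are extreme scenarios: the first needs seven scored stimuli, correlation 0.5 and no rescue effect; the second needs 18 ratings per patient. Correlations, response rate, number of readings and rescue effect are all assumed, so the actual size is unknown. The case for changing the plan is that patient deletion stays near 5% in every scenario tried, and the sponsor cannot know beforehand which one applies.

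**What to change.** Add two statements to section VII:

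1. The jackknife for Pk and for differences in Pk deletes one patient, with all of that patient's readings, at a time. It uses n − 1 degrees of freedom, where n is the number of patients analysed.
2. Any paired t-test comparing qNOX, qCON and BIS uses those patient-level pseudo-values or, for raw index values, one value per patient.

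This needs a little programming and no new data. Under the assumptions of step 4, with d = 0 or 1, the SE of a Pk difference becomes 0-13% larger with 3 stimuli and 4-34% larger with 7. It becomes 14-25% smaller if every patient responds exactly once. The chance of declaring Pk 0.80 different from 0.70 changes as follows, at correlation 0.3 and 0.5:

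| Scenario | 3 stimuli | 7 stimuli |
|---|---|---|
| d = 0 | 55 to 51%; 55 to 45% | 88 to 82%; 85 to 68% |
| d = 1 | 56 to 54%; 50 to 47% | 88 to 85%; 83 to 74% |

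Where the single-reading test exceeds its 5% level, part of this apparent loss is only the removal of excess false positives.
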